1.0 Synopsis

Title of Study: Modulation of autophagy: A clinical study of vorinostat plus hydroxychloroquine versus Regorafenib in refractory metastatic colorectal cancer (mCRC) patients.

Investigators: PI: [name] [name]
Statistician: [name]

Study Center(s): UT Health Cancer Center

Concept and Rationale: Colorectal cancer (CRC) is the second most common cause of cancer death in the United States (1). Recently, Regorafenib (RGF), an oral multi-kinase inhibitor with predominant angiogenic or vascular endothelial growth factor (VEGF) inhibition, was approved for patients with mCRC who have progressed on standard therapies, including anti-VEGF agent bevacizumab (2). Compared to placebo, the phase III CORRECT study showed RGF improved median overall survival (mOS) from 5.0 to 6.4 months (mo) and median progression-free survival (mPFS) from 1.7 to 1.9 mo, regardless of K-Ras mutational status (3). Given the modest improvements in survival and clinical studies showing lack of efficacy with continued VEGF inhibition following progression of anti-VEGF therapies, such as bevacizumab, novel therapies continue to be desperately needed in the third-line setting (4). Investigators at our institution have shown that autophagy inhibition using hydroxychloroquine (HCQ) enhanced the apoptotic activity of the histone deacetylase (HDAC) inhibitor, vorinostat (VOR), via ubiquitinated protein accumulation in pre-clinical CRC models (5). Based on this preclinical data, we completed an NIH-funded phase I clinical study evaluating the safety, efficacy, and pharmacokinetics of the combination VOR and HCQ and found that patients with mCRC obtain prolonged clinical benefit with the combination therapy with VOR and HCQ (6). This study led to a Phase II single-arm study of VOR 400 mg PO (orally) daily plus HCQ 600 mg PO daily in patients with mCRC, which has completed accrual of a planned 18 patients but follow-up is presently on going. To date, 5 patients have received 6+ cycles (preliminary mPFS of >3 months), further supporting its activity in mCRC.

Further evaluation of biomarkers of autophagy, such as cathepsin D, and biomarkers of VOR, CDKN1A, that correlate with improved efficacy will help identify patients who benefit from autophagy inhibition (6). The expression of high-mobility group box 1 (HMGB1) increases with autophagy in CRC, and HMGB1 acts upon binding to RAGE (“receptor for advanced glucated end products”) (7, 8).

In addition, HDAC has been well-recognized as potential targets for the treatment of numerous aging-related disorders (9) such as cancer (10). Therefore, we plan to evaluate the potential role of biomarkers of aging with the combination of HCQ plus VOR.

These findings support a phase II study VOR/HCQ versus standard therapy RGF in patients failing standard therapies.

We hypothesize that VOR/HCQ will have improved efficacy when compared to RGF in treatment-refractory mCRC patients. This hypothesis is based on the observations that:

1. In refractory mCRC patients, the role of continued VEGF inhibition in mCRC has not been established (4).
2. Only a modest improvement in survival was reported with the use of RGF, an oral multi-kinase inhibitor with predominantly angiogenic inhibition, for mCRC patients who have failed standard therapies (3).
3. Autophagy inhibition enhances vorinostat-induced apoptosis via ubiquitinated protein accumulation in CRC models pre-clinically (5).
4. Clinical activity based on treatment-refractory mCRC patients enrolled in phase I (6) and the ongoing single arm Phase II study of VOR with HCQ therapy suggests a median PFS of > 3 months.

Our overall objective is to answer these questions: will VOR/HCQ be more efficacious than RGF, will VOR/HCQ be safe, and can biomarkers be identified that will predict clinical efficacy of VOR/HCQ and RGF in refractory mCRC patients?

Primary Objective(s):

- To determine the clinical efficacy with progression-free survival (PFS-1) of the combination of VOR plus HCQ when compared to RGF in treatment-refractory mCRC.

Secondary Objective(s):

- To determine the overall survival in refractory mCRC patients receiving VOR plus HCQ when compared to RGF.
- To determine the progression-free survival (PFS-2) of the crossover treatment, which is optional.
- To evaluate the tumor response rate in refractory mCRC patients receiving VOR plus HCQ when compared to RGF.
- To further define the safety of the combination of VOR/HCQ when compared to RGF in treatment-refractory mCRC.
- To identify biomarkers of autophagy and anti-angiogenic inhibition that are associated with clinical efficacy of VOR/HCQ and RGF, respectively, in mCRC.

Primary Endpoint(s):

- PFS-1: measured from the start of the first treatment the patient is randomized to until the date the criteria for progression are met or the date the patient is taken off study for any reason, whichever is shorter.

[figure not shown]
Secondary Endpoint(s):

- OS: measured from the start of treatment on trial until the death of the patient.
- mPFS-2: measured from the start of the crossover treatment (second regimen, which is optional) until the date the criteria for progression are met or the date the patient is taken off study for any reason, whichever is shorter.

- Response: measured as best response, complete response (CR) or partial response (PR), as defined by Response Evaluation Criteria in Solid Tumors (RECIST 1.1) Committee.
- Adverse events: grade 1-5 adverse events according to the National Cancer Institute Common Terminology Criteria for Adverse Events (NCI-CTCAE) v4.0; measured at baseline, each cycle, and at off study date.
- Biomarkers of efficacy of VOR/HCQ and RGF: evaluate biomarkers of autophagy and anti-angiogenic inhibition that are associated with clinical efficacy of VOR/HCQ and RGF, respectively, in mCRC.

Study Design:

This will be a randomized phase II clinical trial of patients with histologic documentation of metastatic colorectal cancer, who have received local and currently approved standard therapies, excluding RGF. We will give VOR 400 mg PO daily and HCQ 600 mg PO daily in 4-week cycles. Patients will require imaging up to 6 weeks prior to enrollment and will be assessed for measurable evidence of mCRC. This will be a randomized, controlled phase II clinical trial of patients with histological documentation of metastatic colorectal cancer, who have received locally and currently approved standard therapies, excluding RGF. Patients will be randomized 1:1 to RGF or VOR/HCQ (see schema below). Also, crossover is optional after first progression on the initial therapy, and based on physician discretion and in the best interest of the patient. If crossover is not done, then the patient will be off study and can go on to receive other treatments.

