Intervention and Mode of Delivery: If randomized to VOR/HCQ arm, we will administer VOR 400 mg PO daily and HCQ 600 mg PO daily in 4-week cycles. If randomized to RGF arm, we will administer RGF 160 mg PO daily for 3 weeks, of a 4-week cycle. Crossover to the other arm will be allowed, and is OPTIONAL, if the patient has disease progression or unacceptable toxicity. The option to get the crossover treatment will be left to the physician discretion, and if in the best interest of the patient.

Duration of Intervention and Evaluation: Follow-up: A repeat CT scan will be performed after 2 cycles of treatment regimen to evaluate response based on RECIST 1.1 criteria. CT scans will be repeated at least every 2 cycles, or 8 weeks, to ensure no progression of disease. Patients will continue VOR/HCQ or RGF until disease progression, unacceptable toxicity, withdrawal of consent by the patient, or decision of physician for patient's best interest. Crossover to the other arm will be allowed, but OPTIONAL, and will be determined by the treating physician for the patient's best interest. Each patient will be followed for 1 year. We will follow the last patient for 12 months, at which time, the study will be completed for data analysis.

Interim analysis: The O'Brien-Fleming procedure will be used to conduct an interim analyses for efficacy when 50% of the patients complete the study. A statistical basis for stopping the study at the first look will be achieved if the test statistic indicates benefit in the VOR/HCQ Arm and exceeds 2.96259, corresponding to a significance level of 0.003.

If the test statistic does not exceed 2.96259 at the first look then the trial will proceed to the final analysis. A treatment effect will be declared significant and beneficial at the final analysis if the test statistic indicates benefit and exceeds 1.96857, corresponding to a significance level of 0.047. If a treatment effect is not declared at the interim analysis, a statistical basis for stopping the study for futility will be attained if the conditional power is less than or equal to 20%.

Statistical Methods:

Analytic plan for primary objective:

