5.3 Treatment Requirements

All eligible patients who consent to this study must have a baseline evaluation (CT or MRI) within 6 weeks of the start of treatment.

Patient must meet all eligibility requirements to be entered onto the protocol.

5.3.1 Duration of Intervention and Evaluation:

Follow-up: A repeat CT scan will be performed after 2 cycles of treatment regimen to evaluate response based on RECIST 1.1 criteria (See Appendix 13.1 for definitions of response) (73). CT scans will be repeated at least every 2 cycles, or 8 weeks, to ensure no progression of disease. Patients will continue on VOR/HCQ or RGF until disease progression, unacceptable toxicity, withdrawal of consent by the patient, or decision of physician for patient's best interest. Crossover to the other arm will be allowed, but OPTIONAL, and will be determined by the treating physician for the patient's best interest. If patient is not given crossover treatment, then the patient will be off study and will be allowed to receive subsequent treatments. Each patient

will be followed for 1 year. We will follow the last patient for 12 months, at which time, the study will be completed for data analysis.

Interim analysis: The O'Brien-Fleming procedure will be used to conduct an interim analyses for efficacy when 50% of the patients complete the study. A statistical basis for stopping the study at the first look will be achieved if the test statistic indicates benefit in the VOR/HCQ Arm and exceeds 2.96259, corresponding to a significance level of 0.003. If the test statistic does not exceed 2.96259 at the first look then the trial will proceed to the final analysis. A treatment effect will be declared significant and beneficial at the final analysis if the test statistic indicates benefit and exceeds 1.96857, corresponding to a significance level of 0.047.

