7.0 Data Collection

Data will be entered into Case Report Forms (CRF), which are currently in paper form.

For each patient on study, the following will be documented:

- Lab values: CBC, CMP, CEA, PTT/INR (when collected)
- PFS-1: measured from the start of the first treatment the patient is randomized to until the date the criteria for progression are met or the date the patient is taken off study for any reason, whichever is shorter).
- OS: measured from the start of treatment on trial until the death of the patient (date of death)
- PFS-2: measured from the start of the crossover treatment (Optional, second regimen) until the date the criteria for progression are met or the date the patient is taken off study for any reason, whichever is shorter.
- Response: measured as best response at any given time: complete response (CR) or partial response (PR), as defined by Response Evaluation Criteria in Solid Tumors (RECIST 1.1) Committee (73). (See Appendix 13.1 for definitions of response).
- Adverse events: the number and grade 1-5 of all adverse events will be documented according to the National Cancer Institute Common Terminology Criteria for Adverse Events (NCI-CTCAE) v4.0; measured at baseline, each cycle, and at off study date.

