10.0 Statistical Section

Analytic plan for primary objective:

mPFS-1: Historically, the mPFS for previously treated mCRC patients treated with RGF is 1.9 mos. We predict VOR/HCQ will improve mPFS to 3.8 months. We expect 5% lost to followup. Assuming a 36-month accrual period with 1 year for follow up, 36 subjects per group are necessary to obtain 80% power. With 5% lost to follow-up the sample size required per group is 38 ($=36/0.95$), therefore, the total required sample size is 76 subjects. As a result, the target accrual rate is 3-4 patients/month to achieve a target accrual at 36 months with an additional 12month follow-up.

Treatments will be contrasted with regard to PFS-1 with a proportional hazards model with adjustment for age, sex, race, and the baseline tumor K-RAS status (mutated, wild type); the adjusted hazard ratio, its 95% confidence interval, and the p-value for testing the null hypothesis that the log hazard ratio is zero will be presented. Survival curves will be illustrated with Kaplan-Meier plots. Interactions between treatment and baseline covariates will be explored.

If a patient does not complete Cycle 1 and is off study, then this patient will not be evaluable for efficacy but will be evaluable for toxicity.

Interim analysis: The O'Brien-Fleming procedure will be used to conduct an interim analyses for efficacy when 50% of the patients complete the study. A statistical basis for stopping the study at the first look will be achieved if the test statistic indicates benefit in the VOR/HCQ Arm and exceeds 2.96259, corresponding to a significance level of 0.003. If the test statistic does not exceed 2.96259 at the first look then the trial will proceed to the final analysis. A treatment effect will be declared significant and beneficial at the final analysis if the test statistic indicates benefit and exceeds 1.96857, corresponding to a significance level of 0.047. If a treatment effect is not declared at the interim analysis, a statistical basis for stopping the study for futility will be attained if the conditional power is less than or equal to 20%.

Analytic plan for secondary objectives:

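### PFS-1 ends at progression or any off-study exit, but the plan never says which endings are events and which are censored, and it does not name death as a PFS event

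*Combined protocol and SAP*

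**What the plan says.** The Synopsis measures PFS-1 from the start of the first randomised treatment "until the date the criteria for progression are met or the date the patient is taken off study for any reason, whichever is shorter". Sections 5.7 and 7.0 repeat this, and PFS-2 uses the same end point from the start of crossover treatment. Death is named only for overall survival; Section 7.0 has "OS: measured from the start of treatment on trial until the death of the patient (date of death").

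Section 10.0 states: "Treatments will be contrasted with regard to PFS-1 with a proportional hazards model", adjusted for age, sex, race and K-RAS status, with Kaplan-Meier plots. It gives no event or censoring rule. Its one rule about leaving the study is: "If a patient does not complete Cycle 1 and is off study, then this patient will not be evaluable for efficacy", although the patient remains evaluable for toxicity.

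Section 5.3.1 continues treatment until progression, "unacceptable toxicity, withdrawal of consent by the patient, or decision of physician" in the patient's best interest. It adds: "If patient is not given crossover treatment, then the patient will be off study", free to receive other treatment.

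The Synopsis describes crossover in two ways. Under Study Design, "crossover is optional after first progression on the initial therapy". Under Intervention and Mode of Delivery, "Crossover to the other arm will be allowed, and is OPTIONAL, if the patient has disease progression or unacceptable toxicity".

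**The concern.** A proportional hazards model needs an event indicator for every patient. The plan supplies a duration and no indicator, so two analysts could follow it faithfully and obtain different primary results from the same data.

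Exits without progression are built into the design. Three of the four reasons for stopping treatment are not progression, a patient who stops and does not cross over is off study, and Sections 6.0 and 8.0 take a patient off study for hydroxychloroquine eye toxicity. The documents describe no blinding or masked scan review, and an exit can follow a physician's decision.

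Two linked rules touch the same endpoint. The Cycle 1 sentence can remove patients who die early, or who progress early on clinical grounds or an unscheduled scan, from the primary comparison. Also, nothing stops the PFS-1 clock at crossover, so if a patient crosses over for toxicity it could run into the second regimen.

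**Working it through.** **1. The plan's own figure.** Inputs from Section 10.0: medians 1.9 and 3.8 months, 80% power, 36 months' accrual plus 12 months' follow-up, 5% loss. Two-sided 5% is assumed; the sample-size text states no level.
- Hazard ratio = 1.9/3.8 = 0.50.
- Freedman events = (1.960 + 0.842)² × [(1 + 0.5)/(1 − 0.5)]² = 7.85 × 9 = 70.6, so 71.
- Exponential event probabilities are 0.999 (RGF) and 0.983 (VOR/HCQ), mean 0.991.
- 71/0.991/2 = 35.8, so 36 per group; 36/0.95 gives 38.

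The sample size reproduces. It treats about 99% of patients as PFS events and makes no provision for other exits beyond the 5% loss.

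**2. What each reading counts.**

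| Ending | Exits are events | Exits are censored |
|---|---|---|
| Progression on study | event | event |
| Toxicity, withdrawal or physician exit without progression | event | censored |
| Death on study without documented progression | event, if covered by the any-reason wording | censored |
| Death after exit without progression | not counted; clock already stopped | not counted |

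**3. Size, equal exits (illustration).** The exit rates are assumptions. Let x be the exit probability over 2 months at a constant hazard, so k = −ln(1 − x)/2 per month.
- Progression hazards: ln2/1.9 = 0.365 and ln2/3.8 = 0.182 per month.
- For x = 10%, k = 0.053. With exits as events, hazard ratio = (0.182 + 0.053)/(0.365 + 0.053) = 0.56.
- For x = 20%, k = 0.112, and the hazard ratio is (0.182 + 0.112)/(0.365 + 0.112) = 0.62.
- Share leaving before progression = k/(k + h) × [1 − exp(−12(k + h))], where h is the arm's progression hazard. This is about 13% of RGF and 21% of VOR/HCQ patients at x = 10%, and 23% and 37% at x = 20%.

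Power comes from log-rank simulation with 38 per arm, 12 months' follow-up, exits independent of progression and the plan's final critical value of 1.96857:

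| Assumed exits per 2 months | Exits as events | Exits censored |
|---|---|---|
| none | 82% | 82% |
| 10% | 68% | 76% |
| 20% | 53% | 69% |

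Separate runs of the 10% censored case gave 75% to 77%.

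**4. Size, unequal exits as events, no true PFS difference.** With RGF exits of 10% against 5% for VOR/HCQ, the chance of a significant VOR/HCQ benefit rises from about 2.5% to about 5%. At 25% against 5% it is about 21%. With the arms swapped it falls to about 1.5% and 0.2%.

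**5. Cycle 1 rule.** The planning medians imply 1 − exp(−0.365 × 28/30.44) = 28.5% (RGF) and 1 − exp(−0.182 × 28/30.44) = 15.4% (VOR/HCQ) with a PFS event before day 28. These do not estimate how many patients the rule removes. The first scheduled CT follows two 4-week cycles, about day 56, so most such progressions would not yet be documented, and the rule also requires the patient to be off study. The documents do not allow the number to be estimated.

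**The case against.** The strongest reply is that the wording defines how long PFS-1 is measured, not what counts as an event. The endpoint is called progression-free survival throughout, and Kaplan-Meier plots, a Cox model and a 5% loss allowance all imply some censoring. An exit could therefore simply be the end of observation. That reading is open, but the text does not settle it, and it has the cost shown in step 2.

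A reader might infer more than the documents support:
- That PFS-1 simply is time to treatment failure. That is one of two open readings. The clock also ends at off study, not off treatment, and a patient who stops for toxicity may cross over and stay on study.
- That death is ignored. The any-reason wording can cover a death on study; what is missing is its status, and any provision for deaths after exit.
- That PFS-1 has no end if crossover comes first. It has one, progression or off study; the clock simply keeps running into the second regimen.
- That the Cycle 1 rule discards 29% and 15% of patients. Step 5 shows why not.
- That the definition favours one arm. Both arms have toxicity, and no exit rates are given.

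Two features of the plan help. Dose holds and reductions keep some patients on treatment, and the off-treatment CT (Section 6.0) will document progression for some who leave. Neither gives a status to the remaining exits.

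**Conclusion.** The point stands and must be fixed before analysis: event status for the primary endpoint is undefined, and both available readings depart from PFS. The textual finding needs no assumption. The sizes do: exponential times, exits independent of progression, and assumed exit rates. At 10% to 20% per 2 months, the choice of reading alone moves power by about 8 to 15 percentage points (76 − 68 and 69 − 53, before rounding of the simulated values), and both readings fall below the stated 80%. Bias from unequal exits is possible in either direction. The Cycle 1 exclusion and the crossover inconsistency affect the same endpoint but cannot be sized from the documents.

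**What to change.** In the Synopsis and Sections 5.7, 7.0 and 10.0:
- Define the PFS-1 and PFS-2 event as first RECIST 1.1 progression or death from any cause. Do not count other off-study exits as events; censor them at the last adequate tumour assessment.
- State in advance how new non-protocol therapy, deaths after exit, and progression on an unscheduled off-treatment CT are handled.
- Include all randomised patients who start treatment in the PFS-1 analysis, count progressions and deaths before the end of Cycle 1, and amend the evaluability sentence in Section 10.0 to match.
- Report progression, death or any off-study exit as a labelled time-to-treatment-failure sensitivity analysis.
- Reconcile the two Synopsis statements on when crossover may occur, and state how PFS-1 is analysed if crossover precedes progression.

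**Cost.** This is mainly rewording, and the date of death is already collected for OS. There will be fewer events. With 8-week scans and censoring at the last scan, simulated power is about 72% or 63% at equal exits of 10% or 20%, against about 56% or 37% if exits are events under the same scans and 81% with no exits. Off-treatment scanning needs care. If every exit triggers a CT and exits are unequal (10% or 25% RGF against 5% VOR/HCQ), the false-positive chance is about 3% to 4% or 9%, because one arm is scanned earlier; censoring at the last scheduled scan holds it near 2.5% when exits are independent of progression. If exits tend to precede progression, some informative censoring remains. The sensitivity analysis probes that but does not remove it.

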****Crossover is optional and at the discretion of the physician and in the best interest for the patient**

Number of Patients: Historically, the mPFS for previously treated mCRC patients treated with RGF is 1.9 mos. We predict VOR/HCQ will improve mPFS to 3.8 months. We expect 5% lost to follow-up. Assuming a 36-month accrual period with 1 year for follow up, 36 subjects per group are necessary to obtain 80% power. With 5% lost to

follow-up the sample size required per group is 38 ($=36/0.95$), therefore, the total required sample size is 76 subjects. As a result, the target accrual rate is 2-4 patients/month to achieve a target accrual at 36 months with an additional 12-month follow-up.

Main Criteria for Inclusion/Exclusion: Inclusion

Criteria:

1. Histological documentation of metastatic colorectal cancer (mCRC).
2. ECOG performance status of 0-2.
3. Radiographical documentation of metastatic disease with imaging up to 6 weeks prior to enrollment.
4. Patients with mCRC must have been previously treated with irinotecan and/or oxaliplatin and/or VEGF/EGFR therapy or intolerant to these agents
5. Documentation of K-Ras mutational status
6. Adequate hematologic, renal and liver function (i.e. absolute neutrophil count > 1000/mm³, platelets > 75,000/mm³); creatinine < 2 times the upper limits of normal (ULN) total bilirubin < 1.5 mg/dl, ALT and AST < 3 times above the ULN, ALT and AST can be < 5 times ULN if patients have hepatic involvement.
7. Able to provide written informed consent.
8. Patients with the potential for pregnancy or impregnating their partner must agree to follow acceptable birth control methods to avoid conception. Women of childbearing potential must have a negative pregnancy test within 72 hours prior to receiving the investigational product.
9. Tumor blocks available from previous surgery/biopsy, or if not available, patients willing to have biopsy.

Exclusion Criteria:

1. Patients receiving prior therapy with RGF, VOR, and/or HCQ.
2. Patients with uncontrolled brain metastases. Patients with brain metastases must be asymptomatic and off corticosteroids for at least one week.
3. Due to risk of disease exacerbation, patients with porphyria are not eligible.
4. Due to risk of disease exacerbation, patients with psoriasis are ineligible unless the disease is well controlled, and they are under the care of a specialist for the disorder who agrees to monitor the patient for exacerbations.
5. Patients with previously documented macular degeneration or untreated diabetic retinopathy (stable retinopathy is allowed).
6. Patients who have had chemotherapy or radiotherapy within 2 weeks (6 weeks for nitrosoureas or mitomycin C) prior to entering the study. For investigational targeted therapies, patients will need to clear for 5 half-lives (not applicable to standard of care therapies).
7. Patients may not be receiving any other investigational agents.
8. Patients should not have taken valproic acid or another histone deacetylase inhibitor for at least 2 weeks prior to enrollment.
9. History of allergic reactions attributed to compounds of similar chemical or biologic composition to VOR or HCQ.
10. Uncontrolled intercurrent illness including, but not limited to, ongoing or active infection, symptomatic congestive heart failure, unstable angina pectoris, cardiac

arrhythmia, or psychiatric illness/social situations that would limit compliance with study requirements

11. Major surgery or significant traumatic injury occurring within 21 days prior to treatment.
12. QTc > 500 ms at baseline.
13. Gastrointestinal tract disease resulting in an inability to take oral medication or a requirement for IV alimentation, prior surgical procedures affecting absorption, or active peptic ulcer disease. Patients with NG-tube, J-tube, or G-tube will not be allowed to participate.
14. Pregnant women are excluded from this study because vorinostat has the potential for teratogenic or abortifacient effects. For this reason, women of childbearing potential and men must also agree to use adequate contraception (hormonal or barrier method of birth control) prior to study entry and for the duration of study participation.
15. Should a woman become pregnant or suspect she is pregnant while participating in this study, she should inform her treating physician immediately. Because there is an unknown but potential risk for adverse events in nursing infants secondary to treatment of the mother with vorinostat, breastfeeding should be discontinued.
16. Informed Consent - No study specific procedures will be performed without a written and signed informed consent document. Patients who do not demonstrate the ability to understand or the willingness to sign the written informed consent document will be excluded from study entry.

Inclusion of Women and Minorities:

Both men and women and members of all ethnic groups are eligible for this trial.

Intervention and Mode of Delivery: If randomized to VOR/HCQ arm, we will administer VOR 400 mg PO daily and HCQ 600 mg PO daily in 4-week cycles. If randomized to RGF arm, we will administer RGF 160 mg PO daily for 3 weeks, of a 4-week cycle. Crossover to the other arm will be allowed, and is OPTIONAL, if the patient has disease progression or unacceptable toxicity. The option to get the crossover treatment will be left to the physician discretion, and if in the best interest of the patient.

Duration of Intervention and Evaluation: Follow-up: A repeat CT scan will be performed after 2 cycles of treatment regimen to evaluate response based on RECIST 1.1 criteria. CT scans will be repeated at least every 2 cycles, or 8 weeks, to ensure no progression of disease. Patients will continue VOR/HCQ or RGF until disease progression, unacceptable toxicity, withdrawal of consent by the patient, or decision of physician for patient's best interest. Crossover to the other arm will be allowed, but OPTIONAL, and will be determined by the treating physician for the patient's best interest. Each patient will be followed for 1 year. We will follow the last patient for 12 months, at which time, the study will be completed for data analysis.

Interim analysis: The O'Brien-Fleming procedure will be used to conduct an interim analyses for efficacy when 50% of the patients complete the study. A statistical basis for stopping the study at the first look will be achieved if the test statistic indicates benefit in the VOR/HCQ Arm and exceeds 2.96259, corresponding to a significance level of 0.003.

If the test statistic does not exceed 2.96259 at the first look then the trial will proceed to the final analysis. A treatment effect will be declared significant and beneficial at the final analysis if the test statistic indicates benefit and exceeds 1.96857, corresponding to a significance level of 0.047. If a treatment effect is not declared at the interim analysis, a statistical basis for stopping the study for futility will be attained if the conditional power is less than or equal to 20%.

Statistical Methods:

Analytic plan for primary objective:

- mPFS-1: Historically, the mPFS for previously treated mCRC patients treated with RGF is 1.9 mos. We predict VOR/HCQ will improve mPFS to 3.8 months. We expect 5% lost to follow-up. Assuming a 36-month accrual period with 1 year for follow up, 36 subjects per group are necessary to obtain 80% power. With 5% lost to follow-up the sample size required per group is 38 ($=36/0.95$), therefore, the total required sample size is 76 subjects. As a result, the target accrual rate is 2-4 patients/month to achieve a target accrual at 36 months with an additional 12-month follow-up.

Interim analysis: The O'Brien-Fleming procedure will be used to conduct an interim analyses for efficacy when 50% of the patients complete the study. A statistical basis for stopping the study at the first look will be achieved if the test statistic indicates benefit in the VOR/HCQ Arm and exceeds 2.96259, corresponding to a significance level of 0.003. If the test statistic does not exceed 2.96259 at the first look then the trial will proceed to the final analysis. A treatment effect will be declared significant and beneficial at the final analysis if the test statistic indicates benefit and exceeds 1.96857, corresponding to a significance level of 0.047. If a treatment effect is not declared at the interim analysis, a statistical basis for stopping the study for futility will be attained if the conditional power is less than or equal to 20%.

Analytic plan for secondary objectives:

- OS: The analyses of median OS will be performed in the intent-to-treat population. OS will be illustrated with Kaplan-Meier plots, the estimate of median OS with its 95% confidence interval.
- mPFS-2: The analyses of median PFS-2 will be performed in the crossover population (crossover is optional). mPFS-2 will be illustrated with Kaplan-Meier plots, the estimate of median PFS-2 with its 95% confidence interval. Treatment groups will be contrasted with regard to the response rate with a logistic regression model adjusted for age, sex, race and the baseline tumor K-RAS status (mutated, wild type); the odds ratio, its 95% confidence interval, and the p-value for testing the null hypothesis that the log odds ratio is zero will be presented. If the logistic model fails due to small cell counts then treatments will be contrasted with regard to response using Fisher's Exact Test.
- Response rates: Response rates will be measured as the proportion of patients with the best response, complete response (CR) or partial response (PR), as defined by RECIST 1.1 Criteria and a 95% confidence interval.
- Adverse events: All adverse events will be listed by type and grade.

- **Biomarkers of efficacy of VOR/HCQ and RGF:** The significance of variation in biomarkers with treatment will be assessed with linear models with and without adjustment for age, sex, race and the baseline tumor K-RAS status (mutated, wild type). The dependent variables will be log transformed (base 2) if necessary. The relation between treatment efficacy, as measured by PFS-1, and biomarkers will be assessed with proportional hazards models in terms of treatment, the biomarker, the biomarker by treatment interaction, age, sex, race, and baseline tumor K-RAS status (mutated, wild type). Significant effects will be described and illustrated, as appropriate, with Kaplan Meier plots by strata determined by biomarker level and treatment group, for example.

Sample size justification: Historically, the mPFS for previously treated mCRC patients treated with RGF is 1.9 mos. We predict VOR/HCQ will improve mPFS to 3.8 months. We expect 5% lost to follow-up. Assuming a 36-month accrual period with 1 year for follow up, 36 subjects per group are necessary to obtain 80% power. With 5% lost to follow-up the sample size required per group is 38 ($=36/0.95$), therefore, the total required sample size is 76 subjects. As a result, the target accrual rate is 2-4 patients/month to achieve a target accrual at 36 months with an additional 12-month follow-up.

Funding, Regulatory, and Feasibility Issues: The study will be funded by a CPRIT grant. We previously obtained VOR through Merck Pharmaceuticals for both our phase 1 and 2 studies. However, with VOR coming off patent in late 2014, the purchase of generic VOR at low cost is likely. HCQ is already being purchased at low market cost ($<\$50/\text{month per patient}$). Thus, the VOR/HCQ combination provides a cost-effective study drug combination. We have a large referral volume of mCRC patients to our institution for consideration of clinical studies, therefore we do not expect problems with enrollment since we currently enroll 3-4 refractory mCRC patients/month onto phase I clinical trials.

Patient Acceptability/Ethics and Consent Issues: The combination of VOR/HCQ will be given in the third-line setting to patients with refractory mCRC failing first- and second-line therapies; therefore, this treatment competes with RGF or best supportive care. Since there is a clear need to identify better treatments to improve survival in mCRC, this study gives patients a treatment that is likely superior, based on preliminary data, when compared to current standard of care. Stopping rules are in place for lack of efficacy, as discussed above. We expect that VOR/HCQ will be well tolerated based on our Phase I and II preliminary data, with no grade 4 or 5 adverse events observed. However, if there is unexpected toxicity, there will be early stopping for toxicity as follows:

Early stopping for toxicity: The stopping rule for toxicity is not based on conditional statistical power but rather on observed adverse events. A toxicity event for the purposes of safety stopping is defined as a grade 4 or 5 toxicity of any kind due to treatment with VOR and/or HCQ. If at any time during the study there are 2 or more grade 5 toxicities that are attributed to VOR and/or HCQ, then the study will be terminated. If $> 50\%$ of patients are having similar type of grade 3 and 4 toxicity, then the study will be

terminated. If HCQ causes grade 4 peripheral retinal toxicity, there will be prompt drug discontinuation and ophthalmologic evaluation, with consideration for termination of study.

Data Safety and Monitoring Board (DSMB): All protocols conducted at UT Health Cancer Center is covered under the auspices of the Institutional Data Safety Monitoring Plan (DSMP). The Institutional DSMP global policies provide individual trials with institutional policies and procedures, as well as monitoring adverse events of study agents that are overseen by the Data Safety Monitoring Board (DSMB). Baseline events and adverse events will be captured using the Master Adverse Events Document for each patient. The PI will work closely with the DSMB to ensure all safety requirements for this study are met. The DSMB will meet every 6 months to discuss the safety update of this study.

